4.3 Protocol Treatment

[figure not shown]

Figure 1: Treatment schema, as described below.

4.3.1 Arm 1

Patients will receive a placebo along the same dosing schedule as the experimental arm (patients randomized to placebo will take the same number of capsules as those assigned to gabapentin).

This will also include standard supportive care for treatment-related pain and mucositis as needed during concurrent chemotherapy and radiation treatment, consisting of the following:

- Viscous lidocaine 2% oral solution
- Oral liquid or solid opioid medications- e.g., morphine, oxycodone. These will be introduced and titrated at the discretion of the treating physician when the patient-reported pain score is ≥ 4 on a 0-10 scale.

4.3.2 Arm 2

Gabapentin will be initiated at a dose of 300 mg to be taken at bedtime of the night prior to the first radiation treatment. During week 1, the dose will be 300 mg three times a day for a total daily dose of 900 mg. Starting week 2, the dose will be 600 mg taken 3 times per day for a total daily dose of 1800 mg. This will continue until one week after the end radiation treatment (week 8). Therapy will then be titrated down to 300 mg three times a day for 1 day, and then discontinued all together. The standard supporting care for treatment-related pain and mucositis described above will also be included.

4.3.3 Adverse Events

Side effects of gabapentin include somnolence, dizziness, peripheral edema, and fatigue. Rarely, patients experience changes in behavior or suicidal ideation. These effects will be evaluated on a weekly basis.

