1.1 INTRODUCTION

1.1.1 Specific Aims

Strategies to minimize and mitigate external beam radiation therapy related mucositis and pain during the treatment of head and neck cancer remain limited. We hypothesize that gabapentin could be used to delay or reduce treatment-related pain, reliance on opioid medication, and improve the quality of life for these patients. The specific aims of this proposed study include the following:

- Evaluate the reduction or delay of mucositis related pain and morbidity with the use of gabapentin in patients with stage III or IV oropharyngeal squamous cell carcinoma undergoing definitive radiation with concurrent chemotherapy as part of their cancer management, compared to standard supportive side effect mitigation – using patient reported quality of life endpoints such as the Patient-Reported Oral Mucositis Symptoms (PROMS) scale.
- Assess morphine-equivalent opioid use in both treatment arms by collecting the patient's narcotic use in the previous 24-hour period at each weekly evaluation during radiation treatment.
- Report on change in Speech and swallow performance, as measured by the Performance Status Scale (PSS) for Head and Neck Cancer Patients.
- Evaluate changes in weight from baseline throughout treatment between the two arms.
- Calculate the proportion of patients who end up requiring a feeding tube by the end of treatment in both arms.
- Evaluate changes in patient-report quality of life using the Functional Assessment of Cancer Therapy Head & Neck (FACT-HN) and PRO-CTCAE metrics.
- Evaluate the adverse events associated with gabapentin.
- Evaluate the severity of radiation mucositis (grade 3-4, CTCAE, v. 4).

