9.2.6 Other Quality of Life Metrics

Patients will be asked to complete the FACT-HN and PRO-CTCAE quality of life forms (see Appendix). The FACT-HN will be assessed at baseline and at the 7-week (final week) of radiation. The PRO-CTCAE will be assessed at baseline and weekly with the PROMS scale.

The change in scores from baseline to the 6-week follow-up timepoint will be used for analysis.

All assessments are summarized in Table 1.

Table 1. Subject assessments.

| Parameters | Prior to Study Therapy | Weekly During Radiation Therapy | At First Follow-up (6-weeks post completion) |
|---|------------------------|---------------------------------|--|
| History and Physical ^a | X | | X |
| Performance status ^a | X | | X |
| Creatinine | X | | |
| PROMS Score ^b | X | X | X |
| HN-PSS Score ^a | X | X | X |
| FACT H&N ^b | X | | X |
| Weight | X | X | X |
| Daily opioid use (in morphine equivalents) ^a | X | X | X |
| Assess if feeding tube has been placed ^a | X | X | X |
| CTCAE and other adverse events ^a | X | X | X |
| PRO-CTCAE questionnaire ^b | X | X | X |

^a Physician or evaluator reported.

^b Patient reported.

REFERENCES

1. Starmer, H.M., et al., *Effect of gabapentin on swallowing during and after chemoradiation for oropharyngeal squamous cell cancer*. Dysphagia, 2014. **29**(3): p. 396-402.
2. Chaturvedi, A.K., et al., *Human papillomavirus and rising oropharyngeal cancer incidence in the United States*. Journal of Clinical Oncology, 2011. **29**(32): p. 4294-4301.
3. Marur, S. and A.A. Forastiere, *Head and neck cancer: changing epidemiology, diagnosis, and treatment*. Mayo Clin Proc, 2008. **83**(4): p. 489-501.
4. Pignon, J.-P., et al., *Meta-analysis of chemotherapy in head and neck cancer (MACH-NC): an update on 93 randomised trials and 17,346 patients*. Radiotherapy and Oncology, 2009. **92**(1): p. 4-14.
5. Trott, A., et al., *TAME: development of a new method for summarising adverse events of cancer treatment by the Radiation Therapy Oncology Group*. Lancet Oncol, 2007. **8**(7): p. 613-24.
6. Moslemi, D., et al., *Management of chemo/radiation-induced oral mucositis in patients with head and neck cancer: A review of the current literature*. Radiother Oncol, 2016. **120**(1): p. 13-20.

7. Epstein, J.B., et al., *Neuropathic and nociceptive pain in head and neck cancer patients receiving radiation therapy*. Head & neck oncology, 2009. **1**(1): p. 1.

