| 50 | Eats only in presence of selected persons in selected places |
| 25 | Eats only at home in presence of selected persons |
| 0 | Always eats alone |
| 999 | Inpatient |

UNDERSTANDABILITY OF SPEECH /____/

- | | |
|-----|--|
| 100 | Always understandable |
| 75 | Understandable most of the time; occasional repetition necessary |
| 50 | Usually understandable; face-to-face contact necessary |
| 25 | Difficult to understand |
| 0 | Never understandable; may use written communication |

NCI CTCAE v4.0 mucositis oral

| Adverse event | Grade 1 | Grade 2 | Grade 3 | Grade 4 | Grade 5 |
|----------------|---|--|---|--|---------|
| Oral mucositis | Asymptomatic or mild symptoms; intervention not indicated | Moderate pain, not interfering with oral intake; modified diet indicated | Severe pain, interfering with oral intake | Life-threatening consequences; urgent intervention indicated | Death |

Oral mucositis is characterized by inflammation of the oral mucosa.

NCI CTCAE: National Cancer Institute Common Terminology Criteria for Adverse Events.

Reproduced from: Common Terminology Criteria for Adverse Events (CTCAE), Version 4.0, June 2010, National Institutes of Health, National Cancer Institute. Available at: http://evs.nci.nih.gov/ftp1/CTCAE/CTCAE_4.03_2010-06-14_QuickReference_5x7.pdf (Accessed October 22, 2013).

NCI PRO-CTCAE™ ITEMS

Item Library Version 1.0

As individuals go through treatment for their cancer they sometimes experience different symptoms and side effects. For each question, please check or mark an in the one box that best describes your experiences over the past 7 days...

1. In the last 7 days, what was the SEVERITY of your DIFFICULTY SWALLOWING at its WORST?

None Mild Moderate Severe Very severe

2. In the last 7 days, what was the SEVERITY of your MOUTH OR THROAT SORES at their WORST?

None Mild Moderate Severe Very severe

In the last 7 days, how much did MOUTH OR THROAT SORES INTERFERE with your usual or daily activities?

Not at all A little bit Somewhat Quite a bit Very much

3. In the last 7 days, what was the SEVERITY of SKIN CRACKING AT THE CORNERS OF YOUR MOUTH at its WORST?

None Mild Moderate Severe Very severe

4. In the last 7 days, what was the SEVERITY of your DIZZINESS at its WORST?

None Mild Moderate Severe Very severe

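### The weekly PRO-CTCAE form names only dizziness among the four common gabapentin effects in section 4.3.3, and the on-treatment dizziness scores have no stated analysis

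*Combined protocol and SAP*

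**What the plan says.** Among the specific aims (section 1.1.1) is "Evaluate the adverse events associated with gabapentin". PRO-CTCAE appears there under a different aim, the one on quality of life.

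Section 4.3.3 names the effects: "Side effects of gabapentin include somnolence, dizziness, peripheral edema, and fatigue". It continues: "Rarely, patients experience changes in behavior or suicidal ideation. These effects will be evaluated on a weekly basis". It does not say with which instrument.

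On the patient form, section 9.2.6 says: "The PRO-CTCAE will be assessed at baseline and weekly with the PROMS scale". Table 1 adds the first follow-up, 6 weeks after radiation. The form in Appendix III includes "In the last 7 days, what was the SEVERITY of your DIZZINESS at its WORST", with a companion question on interference. It closes with an open question on other symptoms and five write-in rows, each with a severity rating.

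Clinician-reported adverse events have their own row in Table 1: before therapy, weekly during radiation, and at first follow-up. Section 9.2.5, headed CTCAE version 4, says that events related to gabapentin will be reported. The only between-arm test in that section is Fisher's exact test, for grade 3-4 mucositis.

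For the forms in section 9.2.6, the one analysis stated is change from baseline to the 6-week follow-up.

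**The concern.** The protocol names four common effects of the study drug and already has a weekly patient form with graded symptom items. That form asks about one of the four. For the other three, a blank write-in row does not show that the patient was asked and had no symptom.

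Tolerability decides whether a reduction in pain is worth having. Fatigue is also a listed radiation effect (section 4.2.10), and sedation a listed opioid effect (section 1.2.2). The trial further hypothesizes that gabapentin lowers opioid use, so less opioid sedation could hide some added somnolence from the drug. For symptoms with this much background, deciding patient by patient which events are drug-related is difficult. Comparing the arms on the same question needs no such decision.

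**Working it through.** The plan gives no figure on this point, so there is none to reproduce. The check is an item count, a map of the capture routes, and a date calculation.

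**1. Item count.** The form's named topics are numbered 1 to 5 without a gap, so nothing suggests that an item was lost from the text.

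| Topic on the weekly form | Fixed questions | Listed in 4.3.3? |
|---|---|---|
| Swallowing difficulty | 1 | No |
| Mouth or throat sores | 2 | No |
| Cracked skin at the mouth corners | 1 | No |
| Dizziness | 2 | Yes |
| Pain | 3 | No |

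Fixed questions: 1 + 2 + 1 + 2 + 3 = 9. Common gabapentin effects with a named item: 1 of 4 (25%).

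**2. Capture routes for the four effects.**

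| Effect | Named patient item, weekly | Patient write-in, weekly | Clinician CTCAE, weekly |
|---|---|---|---|
| Dizziness | Yes | Not needed | Yes |
| Somnolence | No | Optional | Yes |
| Fatigue | No | Optional | Yes |
| Peripheral edema | No | Optional | Yes |

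FACT-HN is not in the text available, so whether it covers fatigue cannot be checked. Neither section 9.2.6 nor Table 1 schedules it weekly.

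**3. Timing of the stated PRO-CTCAE analysis.** Count days from the end of radiation. Section 4.3.2 continues study drug for one week (day 7), followed by one step-down day (day 8). The follow-up is at 6 weeks: 6 × 7 = day 42.

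- Last dose to follow-up: 42 − 8 = 34 days, about 5 weeks.
- The form's recall period is 7 days, so it opens on day 42 − 7 = 35, which is 35 − 8 = 27 days after the last dose.
- Section 7.1 gives an elimination half-life of 5 to 7 hours in normal adults.
- Section 4.4 also mentions a follow-up at 2 ± 1 months. Taking one month as 30 days, the earliest such visit is still 30 − 8 = 22 days after the last dose.

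The stated analysis therefore compares a pre-drug score with a post-drug score. The weekly dizziness ratings collected while patients take the drug do not enter it.

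**4. Attribution.** Section 6 defines an adverse event irrespective of cause and sets out an attribution scale from unrelated to definite. The report promised in section 9.2.5 is of events related to gabapentin. Under section 4.5.4, investigators and assessors are blinded, so this attribution is made without knowing the arm. An event attributed to radiation or opioids would fall outside the report.

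**The case against.** The strongest reply is that the adverse event aim does not rest on this form. The aims and section 9.2.6 both treat PRO-CTCAE as a quality-of-life measure. Gabapentin events belong to section 9.2.5 and to the weekly clinician row of Table 1, and section 4.3.3 commits to evaluating the named effects every week: "These effects will be evaluated on a weekly basis". This stands, and it limits the point to an improvement.

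Three stronger readings are tempting, and the documents support none of them.

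- *The form is unable to capture somnolence, fatigue or edema.* It has five graded write-in rows, so a patient can record and rate any of them. What is missing is a question put to every patient.
- *The clinician record consists only of volunteered complaints.* Section 4.3.3 reads as a planned weekly evaluation of named effects. That no checklist is printed is weak evidence against it, since a protocol need not print its adverse event case report form.
- *Without solicited ratings the drug's contribution cannot be separated from background.* The trial is randomized and double blind. Background fatigue and sedation from other causes are balanced in expectation apart from any effect of the drug on opioid use, and the same blinded staff assess both arms. Incomplete capture costs counts and precision, but a between-arm contrast remains.

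It is also fair to say that the choice of items is a design decision and that the form suits the trial's focus on mucositis and pain. The dizziness item suggests an intention to capture drug effects but does not prove one. The two rare effects in section 4.3.3 need not be solicited on a short symptom form, so they are left out of the count.

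**Conclusion.** The point holds in a limited form. One of the four common gabapentin effects has a named patient item; the other three rely on optional write-in and weekly clinician evaluation. The stated PRO-CTCAE analysis looks about 34 days past the last dose, which leaves the on-treatment dizziness scores without a stated use. Section 9.2.5 makes the gabapentin report depend on attribution.

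The primary endpoint, the sample size and the error rate are not affected, and the adverse event aim is not left without data. How much under-counting results cannot be sized, because the documents give no symptom rates and no capture rates.

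The conclusion assumes that the printed form is the one in use and that the follow-up sentence in section 9.2.6 covers PRO-CTCAE as well as FACT-HN, as its place in that section indicates. It is a worthwhile, inexpensive improvement, somewhere between optional and recommended.

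**What to change.** 1. Add three severity items to the weekly PRO-CTCAE form in Appendix III: drowsiness, fatigue and limb swelling. Use the 7-day recall and five response levels of the dizziness severity item, at the visits where the form is already completed.
2. State in section 9.2.5 or 9.2.6 that, for each of these three and for dizziness, the worst level on the weekly forms completed during radiation will be tabulated by randomized arm, regardless of attribution. Show the baseline level and the number of patients who answered beside it. The table is descriptive: 60 patients at 1:1 is about 30 per arm.

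The cost is three more questions each week (9 + 3 = 12 fixed questions) and one table, with no added visit. The patient's time on the form rises slightly. The dizziness part of the table needs no new data at all.

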4.3.4 Study medication accountability

Patient compliance will be evaluated weekly during clinic visits. Patients are expected to receive 3 doses per day (21 per week), 7 days a week during radiation. Patients who take at least 12 doses a week will be considered compliant. Patients that do not begin gabapentin or require a feeding tube will be followed for the endpoints measured in the protocol for an intent-to-treat analysis.

The investigator is required to maintain adequate records of the disposition of the investigational products. Participants will be asked to return unused tablets at the end of radiation treatment and at first follow-up. The unused tablets will be counted by pharmacy.

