4.5.5 Withdrawal of participants/stopping rules and urgent safety

Participants have a right to withdraw at any time and may be withdrawn at the investigator's discretion. Reasonable effort should be made to contact any participant lost to follow-up. The information collected before the withdrawal will be included in analysis. Participants will not be replaced. The PI will have the authority to deviate from the protocol if doing so relates to the immediate safety of a participant, where continuing to follow protocol would put that participant at risk. If any of the following criteria are met, study enrolment and study therapy will be suspended: death in any participant, where death is attributed in any way to study therapy or intervention; grade 4 anaphylaxis as defined by the World Allergy Organization (WAO).

Study therapies will be discontinued for any of the following reasons: two or more occurrences of grade 3 or above systemic allergic reactions as defined by the WAO; any AE that presents an unacceptable consequence to the participant; an illness that requires treatment not consistent with protocol requirements; inability to comply with the study protocol and pregnancy.

An internal data safety committee will be formed through the Clinical Trials Office and will meet quarterly to review potential adverse effects from the study medication.

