5.1 General Considerations

5.1.1 Dose Modifications for Gabapentin

If patient cannot tolerate gabapentin at the dose specified in this protocol, dose can be reduced in 300 mg (or 1 pill) decrements until side effects subside. If intolerance continues, therapy should be discontinued. Patients who are unable to tolerate the medication will be withdrawn from the study. Patient should be continued to be followed as specified on the protocol, however, for intent-to-treat analysis purposes.

6. ADVERSE EVENT REPORTING:

This study will utilize the NCI Common Terminology Criteria for Adverse Events (CTCAE) version 4.0 for reporting of adverse events (AEs).

Serious Adverse Events (SAE) and adverse events will be carefully recorded, and SAEs will be reported to Henry Ford Hospital's IRB if they meet the IRB's SAE reporting criteria.

Definition of an AE: Any unfavorable and unintended sign (including an abnormal laboratory finding), symptom, or disease temporally associated with the use of a medical treatment or procedure regardless of whether it is considered related to the medical treatment or procedure (attribution of unrelated, unlikely, possible, probable, or definite).

Definition of an SAE: Any adverse experience occurring during any part of protocol treatment and 30 days after that results in any of the following outcomes:

- Death;
- A life-threatening adverse drug experience;
- Inpatient hospitalization or prolongation of existing hospitalization;
- A persistent or significant disability/incapacity;

- Important medical events that may not result in death, be life threatening, or require hospitalization may be considered an SAE, when, based upon medical judgment, they may jeopardize the patient and may require medical or surgical intervention to prevent one of the outcomes listed in the definition. Any pregnancy, including a male patient's impregnation of his partner, occurring on study must be reported to the IRB as a medically significant event. SAEs (more than 30 days after last treatment) attributed to the protocol treatment (possible, probable, or definite) should be reported to the IRB if the reporting criteria is met.

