9.2.4 Opioid Use

Patients with at least 1 reported administration of opioid analgesic will be considered to have received opioid analgesics. The total dose of opioid analgesics will be the sum of all opioid analgesic administrations that have been converted to morphine equivalents (see Appendix II). Use of opioid analgesics will be assessed for a 24-hour period before completing the assessment weekly during radiation. The relationship between analgesic use and treatment-related pain will be evaluated using the general linear model with (at minimum) stratification, treatment arm, and compliance.

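### The compliance rule is a fixed 12 intakes a week: it is not adapted to permitted dose reductions, ignores the amount taken, and feeds the secondary opioid model

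*Combined protocol and SAP*

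**What the plan says.** - **Schedule (4.3.2).** Week 1 runs at 900 mg a day, split over three intakes. The full target then applies: "Starting week 2, the dose will be 600 mg taken 3 times per day for a total daily dose of 1800 mg". Under 4.3.1, "patients randomized to placebo will take the same number of capsules as those assigned to gabapentin".
- **Compliance (4.3.4).** The rule reads: "Patients who take at least 12 doses a week will be considered compliant". The base for that count is given just before it: "Patients are expected to receive 3 doses per day (21 per week), 7 days a week during radiation". Compliance is assessed at the weekly clinic visits, by a method that is not named. Pharmacy counts returned tablets at two points only: when radiation ends and at the first follow-up visit.
- **Dose reduction (5.1.1).** For a patient who cannot tolerate the drug, "dose can be reduced in 300 mg (or 1 pill) decrements until side effects subside". The section does not say whether one step is a pill per day or a pill per intake, how many intakes a reduced dose is split into, or how compliance is then judged.
- **Stopping study therapy (4.5.5).** The listed reasons include "inability to comply with the study protocol and pregnancy".
- **Use in analysis (9.2.4).** The general linear model for opioid use must contain, as a minimum, "stratification, treatment arm, and compliance". How a weekly yes/no status becomes a model term is not stated.
- **Primary analysis (9.1.1).** The repeated measures ANOVA and weekly t-tests on PROMS name no compliance term.

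**The concern.** A compliance variable should tell the analyst either how closely a patient followed the current prescription or how much drug the patient received. Because the base is three doses a day, the count in 4.3.4 is a count of intakes, and it does neither reliably once doses differ between patients. A patient can follow a permitted reduction exactly and still fall below 12. Another can receive well under half of the target amount and still reach 12.

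What is at stake is the opioid model in 9.2.4, where this label is a required term next to treatment arm. Section 4.3.3 lists somnolence, dizziness, peripheral edema and fatigue as effects of gabapentin, so reductions may well be more frequent in that arm, and any mislabelling would then be unequal between arms. The documents give no reduction rates, so the imbalance cannot be sized. The label would also be a poor guide when asking whether a null result reflects the drug or a failure to take it.

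**Working it through.** **Inputs.** 3 intakes a day and a threshold of 12 a week (4.3.4); 300 mg three times daily in week 1 and 600 mg three times daily from week 2 (4.3.2); one reduction step = 300 mg = 1 pill (5.1.1).

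**The plan's own figures.** 3 × 7 = 21 intakes a week; 3 × 300 = 900 mg/day; 3 × 600 = 1,800 mg/day. All reproduce. It follows that the full weekly target is 7 × 1,800 = 12,600 mg, or 12,600 / 300 = 42 capsules, and that the threshold is 12 / 21 = 57.1% of the full intake schedule.

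**Check 1: does a patient who takes every prescribed intake pass?** Intakes per week = 7 × intakes per day, compared with 12. Intakes per day after a reduction are an assumption, since 5.1.1 does not give them.

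| Prescribed dose | Intakes/day | Intakes/week | Label |
|---|---|---|---|
| 1,500, 1,200 or 900 mg/day | 3 | 21 | compliant |
| 1,500, 1,200, 900 or 600 mg/day | 2 | 14 | compliant |
| 600 mg/day | 1 | 7 | not compliant |
| 300 mg/day | 1 | 7 | not compliant |

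At 300 mg/day there is one pill, so 7 is the maximum and the threshold is out of reach. Any other level fails only if taken once daily. If the step is instead one pill per intake, 600 mg three times daily becomes 300 mg three times daily, the count stays at 21, and no fully adherent patient fails.

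**Check 2: how much drug can a compliant week contain?** From week 2, counting only intakes taken whole:

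- Unreduced: 12 × 600 = 7,200 mg; 7,200 / 12,600 = 57.1% of full target.
- Reduced to 300 mg per intake: 12 × 300 = 3,600 mg; 3,600 / 12,600 = 28.6% of full target.

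The 28.6% case arises at 900 mg/day in three intakes with 12 of 21 taken (3,600 / 6,300 = 57.1% of that patient's own prescription). It also arises at 600 mg/day in two intakes with 12 of 14 taken (3,600 / 4,200 = 85.7%). It can arise at 1,200 mg/day in three unequal intakes if the larger ones are skipped. Each case needs both a reduction and missed intakes. In week 1, 12 intakes are 3,600 / 6,300 = 57.1% of that week's schedule.

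**The two checks together.** At 600 mg/day, a patient who takes the whole amount once daily receives 7 × 600 = 4,200 mg a week (33.3% of full target) and is labelled non-compliant. A patient on the same daily dose in two intakes who misses two of 14 receives 3,600 mg (28.6%) and is labelled compliant. The label runs opposite to both adherence and exposure.

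**Check 3: a capsule-based measure.** Keeping the plan's own 57.1% but applying it to capsules prescribed gives 7 × (capsules/day) × 12/21 = 4 × (capsules/day). The weekly cut is then 24 of 42, 20 of 35, 16 of 28, 12 of 21, 8 of 14 or 4 of 7 capsules. A patient who takes everything prescribed passes at every level, on either reading of the reduction step. Exposure still needs its own field: 12 of 21 capsules remains 3,600 mg, 28.6% of full target.

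**The case against.** The strongest reply is that the consequence is small. Compliance appears in one secondary model; the primary analysis does not use it, no per-protocol analysis is planned, and 4.3.4 and 5.1.1 keep patients who never start or cannot tolerate the drug in follow-up for intent-to-treat. Section 1.2.2 describes gabapentin as well tolerated in general, and no figure shows how many patients would reach one pill a day. All of this stands and limits the point to the opioid analysis.

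Several stronger readings are tempting, and the documents do not support them:

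- *That fully adherent reduced-dose patients are labelled non-compliant as a rule.* Divided doses pass, and the problem disappears if the step is per intake.
- *That the plan routinely calls patients on under a third of the dose compliant.* At the unreduced dose, 12 whole intakes give 57.1%. The lower figure combines a reduction with missed intakes and is measured against the full target, not the patient's own prescription.
- *That one of two capsules at every intake scores as 21 doses.* That would be 21 × 300 = 6,300 mg, or 50%, but it depends on a partial intake counting as a dose. The term is undefined, so this is an ambiguity and not a shown misclassification.
- *That falling below 12 leads to stopping study therapy under 4.5.5.* No text links the two, and a reduction allowed by 5.1.1 can fairly be seen as following the protocol.
- *That this count is the only record of exposure.* Pharmacy also counts returned tablets. Two cumulative counts cannot, however, confirm status week by week, and 4.3.4 does not claim that they do.

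**Conclusion.** The point holds in a limited form. Section 4.3.4 sets a fixed count that 5.1.1 does not adapt and that takes no account of dose. Mislabelling of a fully adherent patient is certain only at one pill a day (7 intakes against 12) or on another once-daily schedule, and it assumes that the reduction step is per day. The dose-blindness does not depend on that assumption: from week 2, a compliant week at the threshold can mean 57.1% or 28.6% of the full target, the latter only after a reduction plus missed intakes.

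The analytic effect is on the 9.2.4 opioid model alone. How many patients are affected, and how unequally by arm, cannot be computed from the documents.

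A related limitation remains however compliance is defined. It is observed after randomization and is related to tolerability, so including it beside treatment arm can bias the arm comparison.

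**What to change.** 1. **4.3.4.** Define weekly compliance as capsules taken divided by capsules prescribed at the patient's current blinded dose level. If a yes/no label is wanted, state the cut as a fraction of that ratio. Say how weeks after study drug has been discontinued are coded, since nothing is then prescribed and the ratio is undefined. Placebo patients take the same number of capsules, so the definition works identically in both arms without unblinding.
2. **Exposure.** Record the current dose level (capsules per day) and capsules taken (mg-equivalent) as separate weekly fields.
3. **9.2.4.** Use the redefined variable, and state how weekly values enter the model. Also report the opioid comparison between arms without compliance.
4. **Reconcile 4.3.4, 4.5.5 and 5.1.1.** The sections should agree on what one reduction step means, how a permitted reduction bears on compliance, and whether compliance as defined has any bearing on the inability to comply listed in 4.5.5. No dose or stopping rule is proposed here; that is for the investigators.

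**Cost.** A wording change, two case report form fields, and a capsule tally by patient report or bottle check at weekly visits already scheduled. The only added burden is the weekly tally; patients would need to bring their bottles if that method is chosen.
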